14. BMI <16
15. BMI ≥40
16. Celiac disease
17. Documented C difficile colitis within four weeks of screening
18. Diabetes Mellitus requiring medication
19. Albumin<2.0mg/dl, within 4 weeks of screening (if tested as part of routine clinical care)
20. Known allergy to tree nuts or peanuts
21. Other conditions that would be a contraindication to any of the study diets or preclude the participant from completing the study.
22. Currently participating in another clinical trial of a drug to treat IBD or a dietary therapy for any indication.

\*Patients may continue these medications at stable dose for the first six weeks and budesonide may be used at any dose. After the 6th week in the study, patients may taper their steroid dose. The study will provide a recommended taper schedule.

\*\*Loading/induction doses of biologic type medication will be considered a stable doses.

\*\*\*Exception for treatment failures: if a subject is determined to fail on any of the following standard lines of treatment at the treating investigator's discretion, subjects may screen for study intervention based upon the following wash out periods: 4 weeks for thiopurine and methotrexate and 8 weeks for natalizumab, vedolizumab, anti-TNF, or ustekinumab.

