#### **6.2.5 End of Study Visit**

The end of study visit will take place at week 12 or at the visit where the participant withdraws or is withdrawn from the study. This visit will include a physical exam to obtain CDAI score. An sCDAI score will also be calculated. Participants will be asked to collect a stool sample at home and ship it to Penn. Stool will be shipped from Penn to LabCorp to obtain an FCP result. Participants will be asked to complete a DHQ, SIBDQ, a 24-hour dietary recall, and provide information about adverse events, medications, joint symptoms and provide health status information (physical, mental and social) to obtain a PROMIS score. Participants will also be weighed and have their blood drawn to measure hsCRP and hematocrit.

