### **6.3 Rescue Therapy [if applicable]**

Participants will remain under the care of their treating gastroenterologist while in the study. If their symptoms worsen, participants will contact their treating gastroenterologist and follow any recommendations with regard to changes in therapy for their Crohn's disease. Participants whose worsening symptoms require a change in the current treatment for Crohn's disease will be considered study treatment failures and will be withdrawn from the study. See Section 6.5 for subject withdrawal information.

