#### **8.4.2 Efficacy Analysis**

Analysis of the primary outcome: The primary analyses for the RCT will use 2-sided tests of statistical significance and will be performed using the intention-to-treat principle. Thus, patients will be classified according to the study arm that they were assigned, regardless of the amount of food from the assigned diet consumed. The primary analysis will compare the proportion of patients who achieve a symptomatic remission (aim 1) at week 6 using the Cochran-Mantel-Haenszel (CMH) chi square test, which is equivalent to the score test derived from the conditional logistic regression. All patients who are withdrawn or lost to follow-up prior to week 6 will be considered treatment failures. The MSD will be considered the reference group for all analyses. Although randomization should minimize unbalance between the groups, it is still possible that unbalance may occur. As such, we will use stratified analyses and logistic regression analysis to adjust for potential unbalance between the two groups as observed in

the descriptive analyses. Age, sex, smoking status, duration of CD, presence of disease involving the colon and/or rectum, use of corticosteroids during the trial, current use of biologic therapy, and current use of immunomodulator therapy will be examined individually for potential confounding of the main outcome using logistic regression analysis. All variables that affect the crude estimate of the relative risk of effectiveness by 10% or greater will be included in the final model.

Stratified analyses will be used to assess for treatment effect heterogeneity based on the following variables: presence of documented inflammation at baseline (defined as FCP>250 mcg/g, hsCRP >5 mg/L). Although pre-specified, we have not powered the study for these subgroup analyses and as such they will be considered hypothesis generating. Therefore, we will report the overall results as well as results for each subgroup. We note that the strongest a priori hypothesis for treatment effect heterogeneity is with the presence or absence of inflammation. We hypothesize that the SCD may appear relatively more effective among those patients without active inflammation than among those with confirmed active inflammation at baseline.

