#### **5.5.1. Outcome definitions**

Clinical remission will be defined use the sCDAI which provides a composite measure of relevant patient reported outcomes (PROs). Symptomatic remission will be defined as a sCDAI <150^4 in the absence of the need for increasing corticosteroid dose or initiation of new therapies for CD during the study period. Participants who withdraw from the study prior to week 6 will be categorized as failing to achieve symptomatic remission and other related outcomes.

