### **5.5.2. Statistical analysis for primary and secondary outcome measures**

The primary analysis will compare the proportion of patients who achieve a symptomatic remission (aim 1) and reduction of inflammation (aim 2) at week 6 using the Cochran-Mantel-Haenszel (CMH) chisq test, which is equivalent to the score test derived from the conditional logistic regression with treatment

strata as the conditioning factor. All patients who are withdrawn or lost to follow-up prior to week 6 will be considered treatment failures. The MSD will be considered the reference group for all analyses. Although randomization should minimize unbalance between the groups, it is still possible that unbalance may occur. As such, we will use stratified analyses and conditional logistic regression analysis to adjust for potential unbalance between the two groups as observed in the descriptive analyses. Age, sex, smoking status, duration of CD, presence of disease involving the colon and/or rectum, use of corticosteroids during the trial, current use of biologic therapy, and current use of immunomodulator therapy will be examined individually for potential confounding of the main outcome using logistic regression analysis. All variables that affect the crude estimate of the relative risk of effectiveness by 10% or greater will be included in the final model.

Stratified analyses will be used to assess for treatment effect heterogeneity based on the following variables: duration of CD (as EEN appears to work better in newly diagnosed patients), presence of colonic and/or rectal disease (EEN has been hypothesized to work better in patients with only small bowel disease), and use of corticosteroids during the trial (these patients may have more severe disease). We will use the logistic regression models to look for evidence of treatment-covariate interactions. Although pre-specified, we have not powered the study for these subgroup analyses and as such they will be considered hypothesis generating. Therefore, we will report the overall results as well as results for each subgroup. We note that the strongest a priori hypothesis for treatment effect heterogeneity is with the presence or absence of inflammation. We hypothesize that the SCD may appear relatively more effective among those patients without active inflammation than among those with confirmed active inflammation at baseline.

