Analysis of secondary outcomes (Secondary Aim 1): hsCRP data will be analyzed in the same manner as FCP data.

Analysis of secondary outcomes (Secondary Aim 2): The secondary outcomes of clinical remission as assessed by the CDAI, PRO2, PRO3 and combined clinical remission and resolution of inflammation will be analyzed using the same methods described for the primary outcomes. We will compare PROMIS scores at baseline and at the end of the trial using a t-test. If there are meaningful differences in baseline scores between the treatment arms, comparison of the PROMIS measures at the end of follow-up will be adjusted for the baseline value using linear regression.

Analysis of data from the Extension Phase (Secondary Aim 2): After week 6, participants will need to provide for the meals on their own if they choose to remain on the diet. This provides an opportunity to further assess the combined feasibility of the diets in the real world and patients' satisfaction with following the diet. Utilizing results from 24-hour dietary recalls, we will determine the proportion of patients assigned to each arm who elect to remain on the diet through week 12. We will also determine the proportion of patients who were able to discontinue steroid use by week 12 among the subgroup who were taking steroids in weeks 1-6. Finally, we will assess reasons for discontinuation of the diet among those who did not continue. Comparisons will be made using Fisher's exact test following the principle of intention to treat. The analysis will be repeated among the subgroup of participants who achieved remission by week 6. These results will be qualitatively compared to the free text data on satisfaction and personal experience with the diets.

Change from baseline stratified by treatment arm: For continuous outcome measures, such as sCDAI, PRO2, PRO3, and FCP, we will compare the week 6 and week 12 values to the baseline value using the Wilcoxon sign rank test, a nonparametric paired test. These analyses will be conducted separately for each treatment group. Imputation of missing data for this analysis will assume that the worst case scenario that the outcome measure was worse during follow-up than at baseline. (Note that approach to missing data for other analyses are described below).

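### Steroid use during the trial serves as an adjustment covariate and subgroup factor although, as worded, it includes post-randomisation starts that define failure; the SAP subgroup list also drops the protocol's baseline-inflammation factor

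*Combined protocol and SAP*

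**What the plan says.** Protocol 8.4.2 and SAP 5.5.2 give the same list of candidate covariates for the adjusted analysis of the main outcome. It includes "presence of disease involving the colon and/or rectum, use of corticosteroids during the trial, current use of biologic therapy". Biologic and immunomodulator use are worded as current use; steroid use is not. The entry rule is: "All variables that affect the crude estimate of the relative risk of effectiveness by 10% or greater will be included in the final model".

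SAP 5.5.2 then lists three subgroup factors: disease duration, colonic or rectal disease, and "use of corticosteroids during the trial (these patients may have more severe disease". Protocol 8.4.2 lists one, documented inflammation at baseline, with cut-offs of FCP >250 mcg/g and hsCRP >5 mg/L. The two lists share no factor. Yet the SAP paragraph goes on to call inflammation its strongest a priori heterogeneity hypothesis.

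Four other places bear on the steroid term:

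- SAP 5.5.1 defines remission as sCDAI <150 "in the absence of the need for increasing corticosteroid dose or initiation of new therapies for CD during the study period".
- Protocol 6.3 says that participants whose worsening requires a change in Crohn's treatment "will be considered study treatment failures and will be withdrawn from the study".
- Protocol 6.2.5 has participants attend a visit at withdrawal "and provide information about adverse events, medications, joint symptoms and provide health status information", so a steroid start can be recorded.
- The footnote to protocol 4.2 covers steroid users at entry: "Patients may continue these medications at stable dose for the first six weeks".

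**The concern.** A covariate or subgroup factor in a randomised comparison should be fixed before the diets can affect it. As worded, this one mixes two groups: participants on a steroid at entry, and participants who start one afterwards. Anyone in the second group who starts for Crohn's disease before week 6 has failed by definition, but stays in the intention-to-treat set. The variable therefore carries part of the outcome. The window also runs to week 12, past the week-6 endpoint.

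The trial is open label, so the tendency to start a steroid when a participant is failing could differ between arms. If it does, stratifying on the variable or adjusting for it moves the diet estimate away from the randomised one and can create an apparent diet-by-steroid interaction.

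Separately, two different subgroup lists leave it unclear which heterogeneity analyses are pre-specified. Nor do the documents say whether the FCP and hsCRP criteria are joined by *and* or *or*.

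**Working it through.** **The plan's own figure.** SAP 5.2 states 80% power with 97 per arm for 40% versus 60%, two-sided 5%, chi-square test. n = [1.96·√(2·0.5·0.5) + 0.8416·√(0.4·0.6 + 0.6·0.4)]² / 0.2² = (1.386 + 0.583)² / 0.04 ≈ 97, and power at 97 per arm is 80.0%. It reproduces, and nothing here changes it.

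**Inputs for the illustration.** From the documents: 97 per arm, 40% remission on MSD, 40% versus 60% as the design alternative, and the 10% rule. Assumed, because the documents give no figures: 15% baseline steroid use (10% and 25% also tried), unrelated to remission, and a share *s* of failures among baseline non-users who start a steroid. A user is a baseline user or a starter.

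**Cell probabilities in an arm with remission *p* and baseline use *b*.**

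- Users: remit *bp*; fail *b*(1−*p*) + (1−*b*)(1−*p*)*s*
- Non-users: remit (1−*b*)*p*; fail (1−*b*)(1−*p*)(1−*s*)

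**No diet effect (40% in both arms), *b* = 0.15, *s* = 0.10 on MSD and 0.30 on SCD.**

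- Users who remit: 0.06 in each arm. Users who fail: 0.09 + 0.51×0.10 = 0.141 (MSD); 0.09 + 0.51×0.30 = 0.243 (SCD).
- User remission: 0.06/0.201 = 29.9% versus 0.06/0.303 = 19.8%. OR = 0.141/0.243 = 0.58.
- Non-users who remit: 0.34 in each arm. Non-users who fail: 0.459 (MSD); 0.357 (SCD). OR = 0.459/0.357 = 1.29.
- Mantel-Haenszel RR = (0.06×0.201/0.504 + 0.34×0.799/1.496) / (0.06×0.303/0.504 + 0.34×0.697/1.496) = 0.2055/0.1945 = 1.057.
- Adjusted OR from the logistic fit = 1.10.

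The true value of each ratio is 1.0.

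**Range under no diet effect.** The last two columns give how often the covariate meets the 10% rule in 6,000 simulated trials of 97 per arm.

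| Baseline use | Starts among failures, MSD vs SCD | OR, users | OR, non-users | Adjusted OR | Selected, RR scale | Selected, OR scale |
|---|---|---|---|---|---|---|
| 15% | 10% vs 30% | 0.58 | 1.29 | 1.10 | about 18% | about 49% |
| 15% | 10% vs 20% | 0.73 | 1.13 | 1.04 | 3% | 15% |
| 15% | 10% vs 15% | 0.85 | 1.06 | 1.02 | <1% | 6% |
| 10% | 10% vs 30% | 0.51 | 1.29 | 1.13 | 28% | 63% |
| 25% | 10% vs 30% | 0.68 | 1.29 | 1.06 | 7% | 26% |

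Repeat simulations of the first row gave 17% and 47–48%. Using baseline steroid use alone, selection is under 1% on either scale.

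**Design alternative (40% versus 60%, true OR 2.25), *b* = 0.15.**

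- Starts in 30% of MSD and 10% of SCD failures: adjusted OR 2.07; subgroup ORs 3.88 (users) and 1.75 (non-users).
- Starts in 15% and 10%: adjusted OR 2.22.
- Starts in 20% of failures in both arms: the OR stays at 2.25, but remission reads 24% versus 41% in users and 45% versus 65% in non-users, although it is 40% versus 60% whatever the baseline use.

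**A second parameterisation.** Starts were set instead as a share of all baseline non-users, with 10–30% baseline use and up to 20% versus 5% starting. The largest expected shift in the adjusted RR was from 1.50 to 1.37 (−8.7%), so no expected shift reached 10%. Selection in the table comes from moderate bias plus sampling variation.

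**The case against.** The strongest reply is that baseline use is what was meant. The adjustment targets imbalance seen in the descriptive analyses, which are of baseline data. The SAP's variable tables hold only current and former steroid use. The stated reason, more severe disease, describes entry status. Stable-dose use is allowed to week 6, and the SAP's week-12 analysis refers to those "among the subgroup who were taking steroids in weeks 1-6". This reading is plausible, but no text imposes it. That last phrase does not exclude new starters either, and medications are recorded at follow-up and withdrawal visits, so the literal variable can be built.

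The second reply concerns size, and much of it stands. Equal remission with three times the steroid starts among failures is an assumed case, and the documents do not suggest it. On the relative-risk scale, which the text names, the adjusted estimate moves only to 1.057 even then. The higher selection rates apply only if the rule is run on odds ratios, which the logistic models make possible but the text does not say. A Wald test of the interaction at 5%, under no diet effect, rejects in about 17% of simulated trials at 10% versus 30%, about 8% at 10% versus 20%, and 5% at 10% versus 15%. False interactions are thus a material risk only in the extreme case; distorted subgroup estimates remain in the milder ones. The model is also simple: baseline use is taken as not prognostic, and starts for other conditions or after week 6 are left out.

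Third, the subgroups are labelled hypothesis generating, and the inflammation hypothesis is visible in both documents. Both statements are true and limit the severity. But the SAP commits to reporting each subgroup, and its list still omits the factor that it ranks first.

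**Conclusion.** The concern holds as a should-fix point. Following the text as written conditions a supplementary model and one reported subgroup on a variable that overlaps the failure definition. The primary CMH test, the 97 per arm and the 80% power are untouched.

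Bias in the adjusted estimate is small unless steroid starts among failures differ strongly between arms: 1.02 to 1.10 on the OR scale at 15% baseline use under no effect, and up to 1.13 at 10% baseline use. The subgroup estimates distort more. Even with equal starts, remission rates within the subgroups are misleading. All of these sizes rest on assumed baseline-use and start rates. That the variable overlaps the outcome does not depend on them; it follows from the definitions.

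The subgroup lists are a plain inconsistency, not an omission of the inflammation hypothesis from the plan.

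**What to change.** In SAP 5.5.2 and protocol 8.4.2, define the steroid covariate as corticosteroid use at randomisation, taken from the current-use field in the SAP's baseline table. Use the same definition for the SAP subgroup.

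Make the two subgroup lists identical. Add baseline inflammation to the SAP list, state one rule for combining FCP >250 mcg/g and hsCRP >5 mg/L (either or both), and test it with a treatment-by-factor interaction.

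As a clarification, state whether the 10% rule is applied to the relative risk or the odds ratio.

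The cost is wording in the two documents. The baseline variables are already collected, and no visit, sample or sample-size change is needed.

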### **7.3 Current Symptoms**

Participants' current symptoms, both Crohn's disease-related and otherwise, will be collected at each visit. Crohn's symptoms will also be collected through daily online surveys. Patient reported outcomes using PROMIS and other measures will be assessed at each visit.

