**Analysis of secondary outcomes (Secondary Aim 2):**

The secondary outcomes of clinical remission as assessed by the CDAI, PRO2, PRO3 reduction of hsCRP by >50% and to <5 mg/L, reduction of FCP by >50% and to a value of <250mcg/g and combined clinical remission and resolution of inflammation will be analyzed using the same methods described for the primary outcomes.

The secondary outcomes of fatigue, sleep quality, social aspects and pain interference will be measured using PROMIS short forms using the same methods as previously employed within CCFA Partners. PROMIS items are calibrated using a T score such that 50 is the mean for the general US population with a standard deviation of 10. Higher scores reflect greater level of the domain. We will compare PROMIS scores at baseline and at the end of the trial using a t-test. If there are meaningful differences in baseline scores between the treatment arms, comparison of the PROMIS measures at the end of follow-up will be adjusted for the baseline value using linear regression.

**Analysis of data from weeks 7 – 12 (Secondary Aim 3):** After week 6, participants will need to provide for the meals on their own if they choose to remain on the diet. This provides an opportunity to further assess the combined feasibility of the diets in the real world and patients' satisfaction with following the diet. Utilizing results from 24-hour dietary recalls, we will determine the proportion of patients assigned to each arm who elect to remain on the diet through week 12. We will also determine the proportion of patients who were able to discontinue steroid use by week 12 among the subgroup who were taking steroids in weeks 1-6. Finally, we will assess reasons for discontinuation of the diet among those who did not continue. Comparisons will be made using the CMH test following the principle of intention to treat. The analysis will be repeated among the subgroup of participants who achieved remission by week 6. These results will be qualitatively compared to the free text data on satisfaction and personal experience with the diets.

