#### **5.5.3. Analysis of PROMIS and arthritis measures**

PROMIS measures will be compared at baseline, week 6 and week 8 using a t-test or with adjusted linear regression if there is evidence of confounding despite randomization. Additional analyses will compare change in PROMIS measures from baseline to week 6 and week 12 between groups. The RADAI arthritis screen, RAPID3, and BAS-FI will be treated as a continuous measures and compared between groups similar to the approach for PROMIS.

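### PROMIS and arthritis scores are compared by an unadjusted t-test unless an undefined baseline trigger is met, which loses precision; SAP 5.5.3 also names week 8, when these scores are not collected

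*Combined protocol and SAP*

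**What the plan says.** Secondary objective 3 covers fatigue, pain and joint symptoms. Three places describe the analysis of the scores that serve it.

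- **Protocol 8.4.2 and SAP 5.5.2**, in the same words: "We will compare PROMIS scores at baseline and at the end of the trial using a t-test". Adjustment is conditional. The trigger reads "If there are meaningful differences in baseline scores between the treatment arms", and what then follows is that "comparison of the PROMIS measures at the end of follow-up will be adjusted for the baseline value using linear regression". Neither section says what counts as meaningful.
- **SAP 5.5.3**: "PROMIS measures will be compared at baseline, week 6 and week 8 using a t-test or with adjusted linear regression", the regression being reserved for the case where confounding is found. This is a different trigger, also without a criterion. The section continues: "Additional analyses will compare change in PROMIS measures from baseline to week 6 and week 12 between groups". The RADAI screen, RAPID3 and BASFI are to be "compared between groups similar to the approach for PROMIS".
- **Collection schedule**: protocol 7.3 states "Patient reported outcomes using PROMIS and other measures will be assessed at each visit". The schedule in protocol section 6.1 places PROMIS and joint symptoms at baseline, week 6 and week 12. The follow-up table in SAP section 4 gives weeks 0, 6 and 12 for RAPID-3, BASFI and the PROMIS forms (the timing cell for social isolation is empty). That table does not list RADAI. BASFI is taken only after a positive back-pain screen.

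**The concern.** A baseline value is planned for these scores and predicts the follow-up value. Under the plan, the main score comparison ignores it unless someone judges the arms to differ at baseline. Two things follow.

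First, the comparison is less precise than the data already being collected allow. Chance imbalance is not the main reason to adjust: the baseline removes variance whether or not the arms happen to differ.

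Second, the model depends on a judgement that the plan does not define, and the two triggers are not the same. Two analysts could choose different models from the same data. The plan itself notes, in 8.4.1 and SAP 5.4, that any imbalance arises by chance, so a search for confounding gives no workable rule.

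Separately, the week 8 comparison cannot be carried out as written. SAP 5.5.2 refers to the end of the trial, and SAP 5.5.3 refers to week 8 and, one sentence later, to week 12.

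**Working it through.** **The plan's own figure.** The documents give no power for PROMIS or arthritis scores. The design figure for the primary endpoint reproduces: 40% vs 60%, two-sided 5% and 97 per arm give power 0.800, and 10% vs 30% gives 0.942, against the stated more than 90%.

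**Inputs.**
- 97 per arm, allocated 1:1 (SAP 5.2, protocol 3.3).
- SD 10 T-score points (SAP 5.5.1.5). This is the general US value; the trial's SD is not given.
- Two-sided 5%, stated for the primary analyses and assumed here.
- Baseline to follow-up correlation r: not in the documents, assumed 0.3 to 0.7. Equal variance at baseline and follow-up is also assumed.

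**Formulas.** The standard error of a difference in follow-up means is 10 × √(2/97) = 1.436. The difference detectable with 80% power is (1.960 + 0.842) × 1.436 = 4.02 points. Relative to that t-test, the variance is 1 − r² for ANCOVA and 2(1 − r) for change scores, so the detectable difference is multiplied by the square root of each.

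| r | ANCOVA variance ratio | Detectable, ANCOVA | Change-score variance ratio | Detectable, change score | ANCOVA power at 4.02 points |
|---|---|---|---|---|---|
| 0.3 | 0.91 | 3.84 | 1.40 | 4.76 | 83.6% |
| 0.5 | 0.75 | 3.48 | 1.00 | 4.02 | 89.9% |
| 0.7 | 0.51 | 2.87 | 0.60 | 3.12 | 97.5% |

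At r = 0.5, 97 per arm under ANCOVA carry the information of 97/0.75 ≈ 129 per arm under the t-test.

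**Do the change scores close the gap?** The excess over ANCOVA is 2(1 − r) − (1 − r²) = (1 − r)², which is positive for every r below 1. Below r = 0.5 the ratio 2(1 − r) exceeds 1, so change scores are then worse than the plain t-test.

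**Does the conditional rule recover the loss?** Simulation of 20,000 trials per setting, 97 per arm, reading the undefined trigger as baseline p < 0.05 (an assumption). Adjustment is then used in about 5% of trials.

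| r | Power, two-step rule | Power, ANCOVA always | Type I error, two-step rule |
|---|---|---|---|
| 0.3 | 79.9% | 83.0% | 4.8% |
| 0.5 | 80.8% | 89.6% | 4.3% |
| 0.7 | 81.7% | 97.2% | 3.5% |

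The rule recovers little of the power. A looser trigger would adjust more often and recover more.

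**The case against.** The strongest reply is that nothing here is invalid. In a randomised trial an unadjusted t-test of follow-up scores is unbiased and holds its level. Protocol section 2 calls the secondary aims exploratory, and no power is claimed for these scores. All of that stands, and it makes this an efficiency and prespecification point.

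Three stronger readings are tempting, and the documents do not support them.

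- **That the baseline is otherwise unused.** SAP 5.5.3 plans between-group change-score comparisons without any condition, so the t-test is not the only between-diet test. The missing-data rule also carries the baseline forward. The point is limited to the default score comparison.
- **That the two-step rule inflates the type I error.** Suppose the baseline difference is 1.5 standard errors and is left unadjusted. The follow-up statistic then has mean 1.5r and variance 1 − r², and rejects in 8.2% of null trials at r = 0.5 and 10.1% at r = 0.7. That is a selected case. With no imbalance and r = 0.7 the rate is about 0.6% (1.96/0.714 = 2.74). Over all randomisations the simulated rate is 3.5% to 4.8%.
- **That nothing is measured at week 8.** The daily symptom surveys run to week 12. What is absent is PROMIS and the arthritis measures. The following sentence of SAP 5.5.3 uses weeks 6 and 12, so week 8 is probably a slip.

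It is also fair that the point figures above apply only to T-scores. RADAI, RAPID3 and BASFI have other scales, and BASFI will have fewer than 97 per arm. The factor 1 − r² carries over to them; the values in points do not.

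**Conclusion.** The point holds as one of lost precision, an undefined choice of model and a wrong time point. For PROMIS scores, always adjusting lowers the detectable difference from 4.02 points to 3.84 (r = 0.3), 3.48 (r = 0.5) or 2.87 (r = 0.7), a variance reduction of 9%, 25% or 49%. These figures rest on the assumed correlations and on a general-population SD; a different SD scales every value in points by the same factor and leaves the percentages unchanged. The week 8 conflict needs no assumption: the schedule has no PROMIS or arthritis assessment then. The change is worth making before analysis, but neither the primary comparison nor the validity of the trial depends on it.

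**What to change.** In protocol 8.4.2, SAP 5.5.2 and SAP 5.5.3:

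1. Replace the t-test and both conditional triggers with one prespecified ANCOVA: follow-up score on diet, baseline score and the biologic-use randomisation stratum, fitted whatever imbalance is observed.
2. Apply it at weeks 6 and 12 to all PROMIS domains, RADAI and RAPID3, and to BASFI among participants who screen positive for back pain and have a baseline score. Which of the two weeks is the main one is for the sponsor to state.
3. Change week 8 in SAP 5.5.3 to agree with the week 12 assessment, and add RADAI to the data table in SAP section 4 so that its schedule is explicit.

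The cost is SAP and protocol wording and a few lines of code. No new data are needed.
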